3.2 Rationale for study design, doses and control groups

Patients allocated to RIPC will undergo a RIPC protocol within 60 minutes prior to PCI, according to previously established preconditioning protocols (CRISP stent study).²¹ Antiplatelet doses in the ticagrelor and the control group are according to established practice guidelines (ESC Guidelines for Revascularization 2014).²³

4. SUBJECT SELECTION CRITERIA

A total number of 152 patients (38 patients of each group) will be recruited from patients with stable CAD or NSTEMI-ACS undergoing coronary angiography, eligible for PCI

4.1 Inclusion criteria

For inclusion in the study subjects should fulfill the following criteria:

1. Provision of informed consent prior to any study specific procedures
2. Patients (*Female and male*) ≥ 18 of age
3. Patients with NSTEMI-ACS undergoing coronary angiography, eligible for PCI

4.2 Exclusion criteria

Subjects should not enter the study if any of the following exclusion criteria are fulfilled:

1. Women of childbearing potential
2. Severe comorbidity (estimated life expectancy <6 months)
3. Baseline cTnI before PCI that is not stable or falling or is $> 5 \times 99^{\text{th}}$ percentile URL.
4. End-stage renal disease(eGFR<15 ml/min/1.73 m²)
5. CRUSADE Bleeding Score >50
6. Patients with an indication for oral anticoagulation
7. On maintenance therapy with ticagrelor or those that have received clopidogrel for less than 3 days
8. Use of nicorandil or glibenclamide
9. Concomitant theophylline/aminophylline use
 - I. Known contraindications to the use of ticagrelor Hypersensitivity to the active substance or to any of the excipients
 - II. Active pathological bleeding
 - III. History of intracranial haemorrhage
 - IV. Moderate to severe hepatic impairment
 - V. Co-administration of ticagrelor with strong CYP3A4 inhibitors (e.g., ketoconazole, clarithromycin, nefazodone, ritonavir, and atazanavir).

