1.4 Benefit/risk and ethical assessment

Peri-procedural cardiac troponin elevation has been associated with new irreversible myocardial injury and several studies have reported that peri-procedural injury is associated with worst prognosis. According to the available evidence, the prognostic significance of PMI is more pronounced when pre-procedural troponin is increased, i.e. in the setting of acute coronary syndromes. Data from the Cardiac Remote Ischemic Preconditioning in Coronary Stenting (CRISP Stent) study support that implementation of a RIPC protocol during PCI may reduce major adverse cardiovascular events during long-term follow-up and that post-procedural troponin I concentration associated with the development of major adverse cardiovascular events.²¹ If this protective effect is potentiated with treatment with ticagrelor, patients are expected to further benefit.

Ticagrelor has been shown to reduce significantly the rate of death from vascular causes, myocardial infarction, or stroke in patients with an acute coronary syndrome (ACS) with or without ST-segment elevation, compared to clopidogrel. These benefits were obtained without an increase in the rate of overall major bleeding but with an increase in the rate of non-procedure-related bleeding.²² Accordingly, treatment with ticagrelor in patients undergoing PCI for non ST-segment elevation ACS (NSTEMI-ACS) or ST-segment elevation MI (STEMI) has been approved by the European Medicines Agency (EMA) and carries a Class I level of evidence B recommendation from the European Society of Cardiology (ESC)²³

Even though ticagrelor has not received approval in patients with stable CAD, several clinical trials have assessed its pharmacodynamic and pharmacokinetic effects in comparison with clopidogrel in this patient population, proving superior efficacy in platelet inhibition with a safety profile consistent with previous studies.^{24,25,26,27}

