In treating patients with stable CAD with a more potent antiplatelet drug, lies a risk of increased bleeding, even though according to previous studies this is expected to be minor and non-life threatening (PLATO).²² To minimize patient risk, patients with a CRUSADE [Can Rapid risk stratification of Unstable angina patients Suppress ADverse outcomes with Early implementation of the ACC/AHA guidelines] bleeding risk score >50 will be excluded from the study. Furthermore, duration of ticagrelor treatment will be kept minimal (1 month). Furthermore, since use of ticagrelor is not recommended as part of initial triple anticoagulation therapy, patients with an indication for oral anticoagulation will also be excluded.

Finally, even though all efficacy endpoints of the present study are to be evaluated at 24 hours following PCI, it is considered in the subjects' interest to continue study treatment for a period of a month, during which period all enrolled subjects will be monitored for the safety endpoint and other adverse events. This is a result of a lack of available evidence to support switching from a more potent to a less potent antiplatelet drug within 24 hours of PCI, and a paucity of studies regarding the optimal clopidogrel loading dose when switching from ticagrelor to clopidogrel.²⁷ Furthermore, receiving a loading dose of ticagrelor and within 24 hours a loading dose of clopidogrel combined with peri-procedural anticoagulation, may significantly increase bleeding risk.

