3. STUDY PLAN AND PROCEDURES

3.1 Overall study design and flow chart

The TRIP study will be a randomized, assessor-blind, active comparator-controlled, clinical trial using a 2×2 factorial design, with 1:1 patient allocation to ticagrelor or clopidogrel and within each treatment a 1:1 allocation to RIPC or control.

According to the study plan, patients who are referred for coronary angiography or NSTEMI-ACS may be screened for randomization.

	Day 1/ Screening	Day 2	Day 3	Day 30 (±5days)
Informed consent form	x			
Inclusion criteria	x			
Exclusion criteria	x	x	x	

Medical history	X			X
Concomitant disease	X			X
Concomitant medication	X	X	X	X
Physical examination (vital signs)	X	X	X	X
ECG	X	X		
Local laboratory values	X	X	X	
Randomization	X	X		
Treatment initiation	X			
RIPC		X		
Coronary angiography assessment		X		
PCI		X		

[figure not shown]
Day 1 of the study is defined as the day of randomization to ticagrelor versus clopidogrel. This should be chosen by the investigator to be the day before the scheduled PCI procedure.

Day 2 of the study is defined as the day of randomization to RIPC or control and subsequent (within 1 hour) coronary angiography and PCI.

In patients already treated with clopidogrel for 3 to 7 days, actions performed on Day 1 and Day 2 may be combined into a single day provided that;

- a. Twenty four hours have elapsed between the last dose of clopidogrel and the randomization to the ticagrelor or clopidogrel group, and
- b. There is sufficient time (2-4 hours) between the randomization and subsequent intake of clopidogrel or ticagrelor and the 2nd randomization to the RIPC or control group.

If for unforeseen reasons, PCI is not conducted within the prespecified timeframe the patient should be withdrawn from the study.

* In case of a patient already on clopidogrel for 3-7 days, ticagrelor loading dose is administered on the day of the procedure (24 hours after the last clopidogrel dose), and no 2nd ticagrelor dose is administered. ** In case of a patient already on clopidogrel for 3-7 days, no loading dose of clopidogrel is administered, but the patient ideally receives 75mg clopidogrel 2-3 hours before the procedure.

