5. STUDY CONDUCT

5.1 Subject enrollment, randomization, and initiation of investigational product

According to the study protocol, patients who are referred for coronary angiography or NSTEMI-ACS may be screened for randomization. Subjects meeting the inclusion and none of the exclusion criteria will be evaluated and their demographic, medical history and current clinical characteristics will be recorded.

During the screening period the eligibility check and physical examination will be performed with assessment of vital signs (heart rate and blood pressure measurement). During the screening period obtained local laboratory results should be examined for exclusion criteria (eGFR, HAS-BLED score, cardiac troponin). The subject will then be informed about the study and will sign the Informed Consent Form.

Day 1 of the study is defined as the day of randomization to ticagrelor versus clopidogrel. This should be chosen by the investigator to be the day before the scheduled PCI procedure.

Day 2 of the study is defined as the day of randomization to RIPC or control and subsequent (within 1 hour) coronary angiography and PCI.

In patients already treated with clopidogrel for 3 to 7 days, actions performed on Day 1 and Day 2 may be combined into a single day provided that;

- a. Twenty-four hours have elapsed between the last dose of clopidogrel and the randomization to the ticagrelor or clopidogrel group, and
- b. There is sufficient time (2-4 hours) between the randomization and subsequent intake of clopidogrel or ticagrelor and the 2nd randomization to the RIPC or control group.

In these case patients are 1:1 randomized to ticagrelor or clopidogrel, and undergo the second randomization within 2-4 hours

If for unforeseen reasons, PCI is not conducted within the prespecified timeframe the patient should be withdrawn from the study.

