5.4.2 Doses and treatment regimens

For the ticagrelor group: loading dose 180 mg ticagrelor (2×90mg tablets). Thereafter, 90mg (1 tablet) b.i.d. At the end of the study period, treatment should be continued according to the prescription of the investigator and the attending physician.

For the clopidogrel group: Patients not on clopidogrel - loading dose 300 mg clopidogrel (4×75mg tablets). At the time of PCI an additional 75 mg dose. Thereafter, 75mg o.d. Patients already on clopidogrel – continuation of maintenance dose. At the end of the study period, treatment should be continued according to the prescription of the investigator and the attending physician.

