5.5 Concomitant and post-study treatment(s)

All medications taken by the patient during the treatment period in addition to the study medication, are termed concomitant medication. All concomitant medication taken during the treatment period of the study will be documented on the case report form (trade name, start and stop date and daily dose). Concomitant medication must also be recorded in the patient's records. All prior medications administered within 1 week of enrolment into the study must be documented on the case report form.

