6.2 Data collection at enrolment and follow-up

Screening (in most cases expected to be the same day with first randomization-Day1)

During this period the investigator will evaluate and record

- Indication for coronary angiography or PCI (stable CAD, NSTEMI-ACS)
- Demographics (age, gender, height, weight, body mass index)
- History of risk factors for cardiovascular disease (Diabetes mellitus, dyslipidemia, hypertension, smoking)
- Medical history including history of previous MI, previous PCI, previous CABG, New York Heart Association Class, Canadian Cardiology Society Angina Class
- Prior and concomitant medication
- Physical examination with vital signs (heart rate, blood pressure)
- Electrocardiogram
- Local laboratory values (hemoglobin, complete blood count including platelet count, serum creatinine, AST, ALT, INR, cardiac Troponin I)

Day 2 - Pre-procedural assessment

- Physical examination with vital signs (heart rate, blood pressure). At this time signs and symptoms of bleeding should be specifically examined.
- Local laboratory values (hemoglobin, complete blood count including platelet count, serum creatinine, AST, ALT, INR, cardiac Troponin I)

In the case of patients already on clopidogrel there will be one combined assessment for screening and pre-procedurally.

Day 2 - Preconditioning

- The timing of the last cycle of RIPC in relation to subsequent PCI should be specifically recorded

Day 2 - Peri-procedural

- Angiographic parameters (number of diseased vessels, target vessel, jeopardy score, rentrop score, American heart association lesion type, stenosis severity, acute gain, timi flow score)
- Procedural parameters (access site, stent length, type of stent used, screen time, radiation dose, contrast dose, number of predilations, predilation time, number of postdilations, postdilation time)
- Complications (jailed side branch, dissection)
- ST-segment deviation during balloon occlusion will be monitored as a secondary efficacy variable. It will be defined as the absolute value of ST-segment deviation at 60-80ms after the J-point in mm at the beginning of coronary angiography minus ST-segment deviation at 60-80ms after the J-point in mm during balloon occlusion.

Day 2 - Post-procedural

- Physical examination with vital signs (heart rate, blood pressure). At this time signs and symptoms of access site bleeding should be specifically examined.
- Electrocardiogram

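### Exclusion 7 names only maintenance ticagrelor, so a patient given just a ticagrelor load stays eligible and, if allocated to clopidogrel, gets a second load

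*Combined protocol and SAP*

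**What the plan says.** Section 4.2, exclusion 7, bars patients "On maintenance therapy with ticagrelor or those that have received clopidogrel for less than 3 days". No other entry criterion deals with recent ticagrelor. The items on ticagrelor contraindications cover hypersensitivity, bleeding, intracranial haemorrhage, hepatic impairment and strong CYP3A4 inhibitors.

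Section 5.4.2 treats loading and maintenance as separate phases: 180 mg of ticagrelor first, then 90 mg twice daily. Its rule for the clopidogrel arm is "Patients not on clopidogrel - loading dose 300 mg clopidogrel".

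The visible exceptions all concern earlier clopidogrel. A footnote in Section 3.1 reads "In case of a patient already on clopidogrel for 3-7 days, no loading dose of clopidogrel is administered". Section 5.1 allows the two study days to be combined for patients on clopidogrel for 3 to 7 days, provided that 24 "hours have elapsed between the last dose of clopidogrel and the randomization to the ticagrelor or clopidogrel group".

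Section 1.4 explains why study drug continues for a month instead of being switched at 24 hours. One reason is that "receiving a loading dose of ticagrelor and within 24 hours a loading dose of clopidogrel combined with peri-procedural anticoagulation, may significantly increase bleeding risk". The same section reports a European approval and a Class I guideline recommendation for "treatment with ticagrelor in patients undergoing PCI for non ST-segment elevation ACS".

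**The concern.** The criterion treats the two drugs unequally. A single clopidogrel load the day before makes a patient ineligible, but a single ticagrelor load does not. The trial enrols patients with NSTE-ACS, for whom Section 1.4 describes ticagrelor as approved and recommended at PCI, so a load given before enrolment is plausible.

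Two things are at stake. The first is safety: the dosing rule would add a 300 mg clopidogrel load to a recent ticagrelor load, shortly before an invasive procedure. The second is the drug contrast. Ticagrelor still active at PCI in a clopidogrel-arm patient would pull that arm's troponin towards the ticagrelor arm, if ticagrelor works as the plan assumes. The analysis sets would not remove such a patient. The per-protocol definition in Section 12.1.1 asks for dosing according to the protocol, which this patient had. Section 12.2 in any case places the efficacy analysis in the safety population.

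**Working it through.** **Does the text admit the patient?** Take a patient with NSTE-ACS who has had one ticagrelor load, no maintenance dose and no clopidogrel.

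1. Exclusion 7, ticagrelor part: not on maintenance, so not excluded.
2. Exclusion 7, clopidogrel part: aimed at short clopidogrel exposure. This patient has had none, and Section 5.4.2 plainly expects patients not on clopidogrel to enter.
3. Section 5.4.2, if allocated to clopidogrel: not on clopidogrel, so 300 mg is given.
4. Sections 3.1 and 5.1: the no-load footnote and the 24-hour rule apply to prior clopidogrel only.

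**How wide is the window?** Taking twice daily as about every 12 hours, a patient who continues ticagrelor reaches a maintenance dose about 12 hours after the load and is then excluded. A patient randomised before that point is within about 12 hours of the load, so the two loads would usually fall within 24 hours of each other. They may not if ticagrelor was stopped after the load. Exclusion 3 requires stable or falling troponin, which may use up more of the window; the sampling interval is not stated.

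**What could it do to the drug comparison?** Inputs from Section 12.3: cell means 0.08 and 0.12 ng/mL with RIPC and 0.14 and 0.24 ng/mL without (ticagrelor, clopidogrel), SD 0.20, correlation 0.7, N = 152, dropout 15%.

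- Drug main effect: (0.12 + 0.24)/2 − (0.08 + 0.14)/2 = 0.18 − 0.11 = 0.07 ng/mL.
- The plan's own figure: 2 × (0.20 × 2.80/0.07)² × (1 − 0.7²) ≈ 65.4, so 66 per drug and 132 in all; 132 × 1.15 = 151.8, rounded up to 152. The stated size is reproduced.
- Residual SD: 0.20 × √(1 − 0.7²) = 0.1428.
- Evaluable: 152 × 0.85 ≈ 129, or 64.5 per drug.
- Power with no pre-loaded patients (noncentral t, 124 df, two-sided 5%): 78.9%.

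Let f be the share of the clopidogrel arm that was pre-loaded and k the share of the ticagrelor effect left at PCI. Neither is in the documents, so both are assumed. The diluted effect is 0.07 × (1 − f × k).

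| f | k | Effect (ng/mL) | Power |
|---|---|---|---|
| 0 | any | 0.0700 | 78.9% |
| 1% | 1 | 0.0693 | 78.1% |
| 1% | 0.5 | 0.06965 | 78.5% |
| 1 of 76 (1.3%) | 1 | 0.06908 | 77.8% |
| 1 of 76 (1.3%) | 0.5 | 0.06954 | 78.3% |
| 2% | 1 | 0.0686 | 77.2% |
| 2% | 0.5 | 0.0693 | 78.1% |

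With k = 0, power is unchanged whatever the share.

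**The case against.** The strongest reply is about timing. A reader might infer that the protocol permits the very combination Section 1.4 warns of. The documents do not support that. Section 1.4 discusses switching after PCI: ticagrelor load, procedure with anticoagulation, then a clopidogrel load within 24 hours. Here the clopidogrel load comes on Day 1 and PCI is planned for the next day, because the single-day pathway is written only for patients already on clopidogrel. Procedural anticoagulation would normally follow both loads instead of falling between them. This part of the objection stands. What remains is a similar sequence, with two loads close together shortly before PCI, and some added bleeding risk is plausible though not quantified.

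The second reply is that the case will be rare. The patient must be loaded, consented and randomised before the next dose (or have stopped ticagrelor), pass the troponin criterion, and then be allocated to clopidogrel, which half will be. Drug allocation is open label and recent medication is recorded, so an investigator should see the load and may well regard the patient as already on ticagrelor. The exclusions for a high CRUSADE score, an anticoagulation indication and active bleeding, together with directed bleeding examinations, give further protection. All this lowers the risk, but none of it makes a recent load an exclusion. If investigators can read the criterion in two ways, that is itself a reason to clarify it.

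The flow-chart figure in Section 3.1 is not available here, so it cannot be checked for a rule on prior ticagrelor. Its surviving footnotes mention prior clopidogrel only.

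**Conclusion.** The gap in the wording is real, and no visible text closes it. Severity is minor. The reason to act is a small, avoidable bleeding exposure together with the unequal treatment of the two drugs.

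Power is not the reason. One pre-loaded patient in the clopidogrel arm costs at most about 1.1 percentage points (78.9% to 77.8%), about 0.5 points if half the ticagrelor effect is left at PCI, and none if it has gone. A reader might infer that the drug comparison is materially compromised. The documents do not support that: they do not describe loading before referral, and any larger share of pre-loaded patients would be a guess.

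The conclusion rests on the literal reading of exclusion 7, on doses about 12 hours apart, and on the planning values in Section 12.3.

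**What to change.** Keep both existing parts of exclusion 7 and insert one between them: any ticagrelor dose, including a loading dose, within 3 days before the first (ticagrelor or clopidogrel) randomisation.

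- **Why 3 days.** It mirrors the clopidogrel threshold already in the criterion and comfortably covers the 24 hours named in Section 1.4. A full week would be broader than needed. It would exclude a patient who took ticagrelor 5 days ago and has since had at least 3 days of clopidogrel; that patient gets no clopidogrel load, so the two-load problem does not arise.
- **Why the first randomisation.** The schedule in Section 3.1 rechecks exclusions on Days 2 and 3, when ticagrelor-arm patients have already had their study load. Without the word, the clause could be read as excluding them.
- **How to check it.** Section 5.5 already states: "All prior medications administered within 1 week of enrolment into the study must be documented on the case report form". That record covers the 3 days. Section 6.2 describes screening as "in most cases expected to be the same day with first randomization-Day1"; where it comes earlier, repeat the check on Day 1.

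The cost is one clause and no new data. A few recently loaded NSTE-ACS patients become ineligible, which may slow recruitment slightly. N stays at 152.

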5. STUDY CONDUCT

5.1 Subject enrollment, randomization, and initiation of investigational product

According to the study protocol, patients who are referred for coronary angiography or NSTEMI-ACS may be screened for randomization. Subjects meeting the inclusion and none of the exclusion criteria will be evaluated and their demographic, medical history and current clinical characteristics will be recorded.

During the screening period the eligibility check and physical examination will be performed with assessment of vital signs (heart rate and blood pressure measurement). During the screening period obtained local laboratory results should be examined for exclusion criteria (eGFR, HAS-BLED score, cardiac troponin). The subject will then be informed about the study and will sign the Informed Consent Form.

Day 1 of the study is defined as the day of randomization to ticagrelor versus clopidogrel. This should be chosen by the investigator to be the day before the scheduled PCI procedure.

Day 2 of the study is defined as the day of randomization to RIPC or control and subsequent (within 1 hour) coronary angiography and PCI.

In patients already treated with clopidogrel for 3 to 7 days, actions performed on Day 1 and Day 2 may be combined into a single day provided that;

- a. Twenty-four hours have elapsed between the last dose of clopidogrel and the randomization to the ticagrelor or clopidogrel group, and
- b. There is sufficient time (2-4 hours) between the randomization and subsequent intake of clopidogrel or ticagrelor and the 2nd randomization to the RIPC or control group.

In these case patients are 1:1 randomized to ticagrelor or clopidogrel, and undergo the second randomization within 2-4 hours

If for unforeseen reasons, PCI is not conducted within the prespecified timeframe the patient should be withdrawn from the study.

